7.3 Study Subjects

7.3.1 *Disposition of Subjects*

Subject disposition will be summarized for all subjects by dose cohort and over all subjects combined. Summaries will include the number and percentage of subjects who signed informed consent, who were enrolled, in each analysis set, as well as discontinuation of the treatment and early termination of the study by the primary reason for discontinuation.

Time on treatment and time on study will be summarized. Time on treatment is defined as (date of last dose – date of first dose + 1)/30.4375. Time on study is defined as (date of last contact – date of first dose + 1)/30.4375.

The number of screen failed subjects will also be presented as well as the reason for their screen failure based on which inclusion/exclusion criteria were not met.

7.3.2 *Protocol Deviations*

Deviations from the protocol and relevant details will be tracked throughout the study and summarized as part of the clinical study report. Major protocol deviations will be defined prior to data base lock and be summarized with the number and percentage of subjects in each category. Deviations will also be given in a by-subject data listing.

7.4 Demographic and Other Baseline Characteristics

7.4.1 *Demographics*

Demographic variables including age, age group (<65 years, \geq 65 years), sex, ethnicity and race, will be summarized by dose cohort and over all subjects combined for the Safety, Efficacy Evaluable, and PP analysis sets.

Age, as collected on the eCRF, will be summarized using descriptive statistics as a continuous variable. Sex, ethnicity, race and age group will be summarized with the number and percentage of subjects in each parameter category.

7.4.2 *Baseline Characteristics*

Baseline characteristics, including weight, height, and body mass index (BMI) will be summarized by dose cohort and over all subjects in the Safety Efficacy Evaluable, and PP analysis sets, using descriptive statistics.

7.4.3 ACC Disease History

ACC disease history will be summarized by dose cohort and over all subjects in the Safety, Efficacy Evaluable and PP analysis sets. The following variables will be included:

- Time since initial diagnosis (months)
- Stage at diagnosis
- Status at screening
- Time since last recurrence/progression (months)
- Site of recurrence/progression
- Bone-only disease
- Bone metastases
- Time since first recurrent or metastatic disease (months).

Time since initial diagnosis, time since last recurrence/progression and time since first recurrent or metastatic disease will be summarized using descriptive statistics. Time will be calculated in months relative to the date of the first infusion. The number and percentage of subjects will be presented by the following: stage at diagnosis, status at screening, site of recurrence/progression, presence of bone-only disease and any bone metastases. A subject will be classed as having any bone metastases if the site of recurrence/progression includes the word bone, hip, sternum, vertebra, rib, and/or skull and/or the site of metastases includes the word bone hip, sternum, vertebra, rib, and /or skull.

Partial initial diagnosis, recurrence/progression and first recurrent or metastatic disease dates will be imputed as follows (to allow times to be calculated for all subjects):

- Missing day will be imputed by the 15th of the month; Missing day and month will be imputed by 1st July.

For the time since first recurrent or metastatic disease, if a subject has Stage IV disease at initial diagnosis with a corresponding M stage of M1 and no date of first recurrent or metastatic disease diagnosis date is recorded, the date of initial diagnosis will be used as the date of first recurrent or metastatic disease (since Stage IV with an M stage of M1 indicates metastatic disease at initial diagnosis).

7.4.4 Prior Cancer Treatment

Prior cancer treatments including prior cancer therapy, prior cancer surgeries, and prior radiation therapy will be summarized by dose cohort and over all subjects in the Safety, Efficacy Evaluable and PP analysis sets.

The following variables will be included:

- Treatment type
- Treatment setting

- Number of previous lines of systemic treatment (including neoadjuvant and adjuvant)
- Best response
- Duration of response
- Reason for discontinuing therapy
- Prior surgery (including types of surgery)
- Time since last surgery (months)
- Prior radiation
- Time since last radiation therapy (months).

Number of lines of previous systemic therapy, duration of prior response, time since last surgery and time since last radiation treatment will be summarized using descriptive statistics. Time will be calculated in months relative to the date of the first infusion. Duration of response is collected on the eCRF.

Partial last surgery/last radiation treatment dates will be imputed as follows:

- Missing day will be imputed by the 1st of the month;
- Missing day and month will be imputed by 1st January.

7.4.5 *Medical History*

The number and percentage of patients reporting any medical history will be summarized by Medical Dictionary for Regulatory Activities (MedDRA) version 23.0 system organ class and preferred term.

7.5 Efficacy Evaluation

7.5.1 *Datasets Analyzed*

All efficacy summaries will be based on the Efficacy Evaluable analysis set (central version for central read outputs) and will be repeated using the PP analysis set for the primary version of each endpoint (the primary version of each endpoint is the first version of the endpoint detailed in each of the sections below, i.e. ORR based on confirmed – local assessment is the primary version of ORR). OS data will also be repeated using the Safety analysis set. A data listing of subjects excluded from any analysis set, to include the reason for exclusion, will be presented.

All efficacy figures will display AL101 4 mg, AL101 6 mg and the total (combined) groups on separate pages.

7.5.2 Primary Efficacy Endpoint Analysis Methods

The primary efficacy endpoint of objective response rate (ORR) will be performed on the Efficacy Evaluable analysis set in each cohort separately. There will be no adjustment for multiplicity based on the two cohorts, as each cohort is considered an independent trial.

The estimate of the ORR will be accompanied by a 2-sided 95% exact binomial confidence interval (CI) derived using the Clopper-Pearson method.

The following sensitivity analyses will be conducted:

- The primary analysis will be repeated using the PP analysis set;
- The primary analysis will be repeated using unconfirmed response;
- The primary analysis will be repeated using central read based on confirmed response;
- The primary analysis will be repeated using central read based on unconfirmed response.

Maximum percentage decrease from baseline in the sum of tumor diameters will be displayed in a waterfall plot, by patient and cohort, for all Efficacy Evaluable subjects.

The estimate of the ORR and associated 2-sided 95% exact binomial CI will also be summarized in tabular format and using forest plots for the following subgroups:

- Prior systemic therapy (yes vs no);
- Time since last recurrence (< 6 months vs \geq 6 months);

□

- Bone only vs. visceral disease;
- Prior radiation vs. no prior radiation;
- Prior systemic chemotherapy vs no prior systemic chemotherapy.

In addition, the following will be provided for best overall response only (i.e., no other endpoints will have summaries by these subgroups):

- a subgroup analysis of median time on treatment and median time on study by best overall response (assessed by the Investigator and irrespective of confirmation). In addition to the normal summary statistics, Q1 and Q3 will also be displayed on this table.

Listings showing local and central read responses (target, non-target and overall responses for RECIST and overall response by MDA) side by side will be included.

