## CURRENT PROTOCOL AMENDMENT SUMMARY OF CHANGES

### AMENDMENT 3 (V4.0); 27 AUGUST 2020

Protocol Section	Summary of Change	Rationale for Change
Protocol synopsis Schedule of Activities (Table 1) 3 Study design 5.4 Biomarkers	
 
Clarify that on-treatment biopsy will be collected (instead of at progression)
 
Clarify that blood samples for biomarkers will be collected on the same day as on-treatment tumor biopsy
 
	
 
To ensure biopsies are collected on treatment and increase compliance to the protocol
 
To allow correlative analysis
 

Protocol synopsis 9.2 Sample size consideration	Clarify text regarding 2 nd look	For clarity purposes
Schedule of Activities (Table 1) 5 Study procedure 5.1.1 RECIST, Table 2	Delete reference to 'Early Discontinuation'	In this study end of study and early discontinuation are synonymous
4.2 Exclusion criteria	
 
Delete exclusion criterion 9
 
Update exclusion criterion 11f (creatinine)
 
	
 
Based on data reanalysis, excluding nucleoside analogues is not supported with clinical or nonclinical data
 
Allow inclusion based on normal creatinine values, as well as sufficient GFR, as
 

Confidential

Protocol Section	Summary of Change	Rationale for Change
		AL101 is not expected to impact renal function
4.5 Early withdrawal of patients from therapy or assessment	
 
Clarify, where relevant, that subjects will be discontinued from IP, not the study.
 
Clarify that subjects being managed with dose interruption for toxicity should have their study assessments followed per SoA.
 
Add reference to dose modifications and toxicity management.
 
	For continued care and safety of subject during the dose interruption
5.2.8 Safety laboratory assessments 6.6 Dose modification and toxicity management guidelines (Table 5)	Add lipase for subjects experiencing $\geq$ Grade 2 diarrhea adverse events	Per request of the Spanish competent authority

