### **Statistical Methods**

#### **Null Hypothesis**

A response rate of 8% or less is considered not clinically significant.

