### **General Statistical Methods**

Statistical analyses will be performed using SAS® v9.4 or higher (SAS Institute, Cary NC, USA).

Evaluation of data will consist primarily of descriptive summary statistics and data listings. Summary statistics for continuous variables will include the sample size (n), mean, standard deviation, median, minimum and maximum. Categorical variables will be summarized in frequency tables. Time to event variables will be analyzed using Kaplan-Meier methods.

If any statistical tests are performed, they will be one-sided, at the 5% significance level. Where confidence limits are appropriate, the confidence level will be 95%, unless otherwise stated.

Individual data (including relevant derived variables) will be presented by parameter in listings. Results of statistical analyses, descriptive summary statistics and supportive listings will also be presented.

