### 9.2 SAMPLE SIZE CONSIDERATION

The study was initiated as a Simon's two-stage optimal design.

The study passed the futility analysis in Stage 1 of the Simon two-stage design and is currently continuing to enroll patients. While the data on Cohort 1 (4 mg QW) is maturing, the study will enroll up to a maximum of 45 patients in Cohort 1 and in parallel will be expanded with the addition of Cohort 2 (6 mg QW). The study will continue enrolling a total of 42 patients in Cohort 2, unless an unexpected safety signal emerges that in the judgement of the DMC requires analysis and/or poses a serious threat to the well-being of the patient. A second look is may be undertaken at 50% of the total information fraction (21 patients) for Cohort 2.

The updated design, a 2-look Group Sequential design with stopping for futility based on Pocock beta-spending function takes the first look after 21 patients and has the following operating characteristics:

	Total n	Stages	1st look n	2nd look n	r1 futility	r2 futility	Power
	42	2	21	42	2	6	89.4

Confidential

Document State: Effective (Controlled)  
CONFIDENTIAL

Page 82 of 118

The expansion of Cohort 1 to a maximum of 45 patients and Cohort 2 to a maximum of 42 patients will provide at least 80% power to test the hypothesis of achieving an increase of the response rate from 8% to 25% using a type I error of 5%.

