7.2 Analysis Populations

The analysis sets are defined as follows:

- Safety analysis set: Includes all subjects who receive at least one infusion of investigational product, including partial infusions.
- Efficacy Evaluable analysis set: Includes all subjects who receive at least one complete infusion of investigational product, have measurable disease at baseline per RECIST v1.1 or modified MDA criteria for bone-exclusive disease and have at least one post-baseline on-study assessment of tumor response (based on local, Investigator read data). This population will be used for the analysis of efficacy data based on local read data and efficacy data which is not dependent on the reader (i.e. overall survival). Baseline summaries will also use this population.
- Efficacy Evaluable analysis set (Central): Includes all subjects who receive at least one complete infusion of investigational product, have measurable disease at baseline per RECIST v1.1 or modified MDA criteria for bone-exclusive disease and have at least one post-baseline on-study assessment of tumor response (based on central read data). This population will be used for the analysis of efficacy data based on central read data only.
- Per-Protocol (PP) analysis set: Includes all efficacy evaluable subjects who have no major protocol deviations as defined by the Sponsor prior to database lock.

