7.9 Determination of Sample Size

The study was initiated as a Simon's two-stage optimal design. The study passed the futility analysis in Stage 1 of the Simon two-stage design and is currently continuing to enroll subjects. While the data on Cohort 1 (4 mg QW) is maturing, the study will enroll up to a maximum of 45 subjects in Cohort 1 and in parallel will be expanded with the addition of Cohort 2 (6 mg QW). The study will continue enrolling a total of 42 subjects in Cohort 2, unless an unexpected safety signal emerges that in the judgement of the DMC requires analysis and/or poses a serious threat to the well-being of the subject. An additional interim look may be undertaken at 50% of the total information fraction (21 subjects) for Cohort 2.

The updated design, a 2-look Group Sequential design with stopping for futility based on Pocock beta-spending function takes the first look after 21 subjects and has the following operating characteristics:

Total n	Stages	1 st look n	2 nd look n	r1 futility	r2 futility	Power
42	2	21	42	2	6	89.4

The expansion of Cohort 1 to a maximum of 45 subjects and Cohort 2 to a maximum of 42 subjects will provide at least 80% power the testing the hypothesis of achieving an increase of the response rate from 8% to 25% using a type I error of 5%.

The futility analysis for Cohort 1 was passed; the futility analysis for Cohort 2 was not conducted.

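### SAP 7.9 sizes Cohort 2 for a one-sided 5% test of 8%, but SAP 7.5.2 reports only a two-sided 95% interval; at 7 responders among 37 to 42 the two disagree, and the SAP does not say which governs

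*SAP*

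**What the plan says.** - **Null value.** Protocol synopsis, Null Hypothesis: "A response rate of 8% or less is considered not clinically significant".
- **Sidedness.** Protocol synopsis, General Statistical Methods: "If any statistical tests are performed, they will be one-sided, at the 5% significance level". SAP 7.9 does not state sidedness.
- **Sizing.** SAP 7.9 claims at least 80% power for "achieving an increase of the response rate from 8% to 25% using a type I error of 5" per cent. Protocol 9.2 describes Cohort 2 as "a 2-look Group Sequential design with stopping for futility based on Pocock beta-spending function takes the first look after 21 patients". Both documents print the same row: n = 21 then 42, r1 = 2, r2 = 6, power 89.4%.
- **What was run.** SAP 7.9: "The futility analysis for Cohort 1 was passed; the futility analysis for Cohort 2 was not conducted".
- **Planned inference.** SAP 7.5.2: "The estimate of the ORR will be accompanied by a 2-sided 95% exact binomial confidence interval (CI) derived using the Clopper-Pearson method". The section names no null value, test, p-value or success count, and does not refer back to r2. Protocol 9.6.2 plans the same interval.
- **Denominator.** SAP 7.2 requires, among other things, that patients "have at least one post-baseline on-study assessment of tumor response (based on local, Investigator read data").

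**The concern.** The sample size rests on a decision rule that the analysis section never applies. The one inferential statement in 7.5.2 is set at a stricter level than the test the cohort is powered for. At one plausible result, the two lead to opposite statements about 8%, and nothing in the SAP says which is the planned conclusion. The trial is open-label, and SAP section 4 says the SAP was updated between the dry-run and database lock. A rule left unstated could therefore be settled after responses are known.

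Two smaller gaps go with this. The cut-off is printed only for n = 42, while the Efficacy Evaluable set may be smaller. The printed power describes a look that did not take place, and no operating characteristics are given for the design as run.

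**Working it through.** **Inputs.** p0 = 0.08 and p1 = 0.25 (synopsis; SAP 7.9); looks at 21 and 42, r1 = 2, r2 = 6, power 89.4% (SAP 7.9). The synopsis stops the study at two or fewer responders at the look, so r is the largest failing count and r2 = 6 means 7 or more passes.

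**1. Reproduce the printed power.** P(pass) = Σ over x = 3 to 21 of b(x; 21, p) × P(X₂ ≥ 7 − x), where X₂ ~ Bin(21, p).
- At p = 0.25: 88.6% (printed 89.4%).
- At p = 0.08: 4.0%.

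Reading r2 so that 6 passes gives power 91.3% but type I error 8.5%, above the stated 5%. So 7 or more is the reading that fits.

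**2. Sidedness.** P(X ≥ 7 | 42, 0.08) = 4.75% without the look and 3.95% with it. Both exceed 2.5%, so r2 = 6 cannot be an upper-tail 2.5% rule. It is consistent with one-sided 5%, as in the synopsis.

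**3. Seven responders, by evaluable n.** One-sided p = P(X ≥ 7 | n, 0.08). The Clopper-Pearson lower limit is the α/2 quantile of Beta(7, n − 6).

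| n | one-sided p | 95% lower limit | 90% lower limit |
|---|---|---|---|
| 36 | 0.022 | 8.19% | 9.50% |
| 37 | 0.026 | 7.96% | 9.23% |
| 40 | 0.038 | 7.34% | 8.51% |
| 42 | 0.047 | 6.97% | 8.09% |

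At 7/42 the full intervals are 7.0–31.4% (95%) and 8.1–29.0% (90%). From n = 37 to 42 the test rejects 8% and the 95% interval includes it; the 90% interval agrees with the test. At n = 34 to 36 both criteria need 7, so there is no conflict. At n = 30 to 33 the same conflict arises at 6 responders.

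**4. How often.** P(X = 7 | n, 0.25) is 11.2% at n = 37 and 7.0% at n = 42.

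**5. Operating characteristics at n = 42.**

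| Rule | Type I error | Power at 25% |
|---|---|---|
| Two looks, 7 or more (as planned) | 4.0% | 88.6% |
| No look, 7 or more (as run) | 4.7% | 92.9% |
| No look, 95% interval must exclude 8% (8 or more) | 1.7% | 85.9% |

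The interval criterion would have power 74.1%, 76.9% and 79.4% at n = 37, 38 and 39.

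**6. Smallest count with exact one-sided p ≤ 0.05.** It is 6 for n = 30 to 33 and 7 for n = 34 to 42. Power at 25% is 79.7% at n = 30, 78.2% at n = 34, 80.8% at n = 35 and 92.9% at n = 42.

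**7. Cohort 1, illustration only.** The documents do not state r1 for Stage 1. A first group of 12 patients appears only in the amendment history. Assuming 12 patients and r1 = 1, 7 of 45 has type I error 4.3% and power 82.2%; 8 of 45 has 1.8% and 79.1%. A single-stage test that ignores Stage 1 would require 8 of 45, because 7 of 45 then has type I error 6.5%.

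**The case against.** The strongest reply is that estimation is the plan. Protocol 9.1 describes the analysis as descriptive, the synopsis sentence on tests is conditional, and SAP 7.5.2 repeats the interval of Protocol 9.6.2. Sizing on a hypothesis and then reporting an estimate with an interval is not an error. SAP 7.1.1 sets two-sided 95% limits, and the SAP takes precedence where the documents differ. This stands in part: estimation may be intended. But 7.9 still claims power to test a hypothesis, and nothing says that r2 was for planning only.

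A reader might infer that the 95% interval is the success rule, so that the cohort is underpowered with 37 to 39 evaluable patients. The documents do not support that, because the interval is nowhere called a success rule. Nor do they support the view that skipping the look harmed the design or was concealed. The look was optional in SAP 7.9, its omission is disclosed there and in 7.5.4.3, and dropping a futility-only look raises power while type I error stays below 5%.

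It is also fair that the conflict arises at a single count and over an assumed range of n. Protocol 4.5 allows some early withdrawals to be replaced, and SAP 7.5.4.2 counts patients without evaluable response data as non-responders. Both limit how far the denominator can fall.

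**Conclusion.** The point holds in a limited form. The sizing rule and the only planned inference sit at different levels, and they disagree about 8% at 7 responders when 37 to 42 patients are evaluable. The SAP does not say which governs. At a true rate of 25% that result has a probability of 7% to 11%. Type I error is not inflated, at least 80% power holds at n = 42 on either reading (92.9% or 85.9%), and the printed 89.4% understates the power of the design as run. The conclusion rests on reading r2 = 6 as one-sided 5%, which the synopsis and the exact tail probabilities support, and on an evaluable number that the documents do not give. Severity: minor to should-fix.

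**What to change.** 1. **SAP 7.5.2, Cohort 2 only.** State that H0: ORR ≤ 8% is tested by an exact one-sided binomial test at the 5% level in the Efficacy Evaluable set. The rejection count is 7 or more of 42; with fewer evaluable patients, it is the smallest count with exact one-sided p ≤ 0.05 (7 for n = 34 to 42, 6 for n = 30 to 33). Show a two-sided 90% interval beside the 95% interval and label the 95% interval descriptive. Record that the 5% level and r2 = 6 come from the protocol version headed "AMENDMENT 3 (V4.0); 27 AUGUST 2020", and that the counts for n below 42 are newly derived from that level.
2. **SAP 7.9.** Keep the planning table and add one line: with the look not conducted, 7 or more of 42 has exact type I error 4.7% and power 92.9%.
3. **Cohort 1.** Do not apply the plain single-stage test. State the rejection count, type I error and power from the actual Stage 1 size and r1.

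Alternatively, if the sponsor intends estimation only, say so in 7.5.2 and label r2 = 6 and the power in 7.9 as planning figures not used for inference.

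The cost is SAP wording, plus one p-value and one extra interval per cohort. Data collection and sample size do not change.

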7.5.3 Secondary Endpoint Analysis Methods

All secondary efficacy endpoints will be analyzed in each cohort independently. There will be no adjustment for multiplicity among the secondary endpoints. The primary analysis of each secondary endpoint will be conducted using the Efficacy Evaluable analysis set. Sensitivity analyses will be conducted using alternative analysis sets as described in each section below.

7.5.3.1 Duration of Response

The Kaplan-Meier method will be used to analyze DOR. The Kaplan-Meier curves will be plotted. Counts and percentages for number of subjects who experienced the event of interest and those who are censored will be presented along with minimum and maximum duration in months. The median, 25th and 75th percentiles will be estimated and their corresponding Brookmeyer-Crowley 95% CIs using the Kaplan-Meier estimates. Landmark estimates will be provided for 2, 4, 6 and 8 months after start of investigational product.

The following sensitivity analyses will be conducted:

- The DOR analysis will be repeated using the PP analysis set;
- The DOR analysis will be repeated using unconfirmed response;
- The DOR analysis will be repeated using central read based on confirmed response;

□

The DOR analysis will be repeated using central read based on unconfirmed response.

Subgroup analyses will not be performed for DOR due to the small number of responders.

DOR will be displayed graphically by patient and cohort using swimmer plots.

7.5.3.2 *Progression Free Survival*

PFS will be summarized similarly to DOR using the Kaplan-Meier method and estimates will be presented along with Brookmeyer-Crowley 95% CIs. Appropriate landmark estimates will also be included.

The following sensitivity analyses will be conducted:

- The PFS analysis will be repeated using the PP analysis set;
- The PFS analysis will be repeated using central read;
- The PFS analysis will be repeated using the subset of subjects with a BOR of PR (BOR will be based on the Investigator results irrespective of confirmation; PFS will be based on the Investigator results).

Subgroup analyses will also be performed based on the main subgroups outlined above for ORR. Kaplan-Meier curves will be plotted for each subgroup.

7.5.3.3 *Overall Survival*

OS will be summarized similarly to DOR using the Kaplan-Meier method and estimates will be presented along with Brookmeyer-Crowley 95% CIs. Appropriate landmark estimates will also be included.

The following sensitivity analyses will be conducted:

- The OS analysis will be repeated using the PP analysis set;
- The OS analysis will be repeated using the Safety analysis set;
- The OS analysis will be repeated using the subset of subjects with a BOR of PR (BOR will be based on the Investigator results irrespective of confirmation).

Additional analyses of OS will be conducted using the same methods as outlined above, with the following changes to the definition of OS:

□

Calculated using date of first recurrent or metastatic disease instead of date of first infusion as time 0 (the same rules as detailed in Section 7.4.3 will be used to impute partial dates and in some cases, missing, dates);

- Calculated using date of initial ACC diagnosis instead of date of first infusion as time 0 (the same rules as detailed in Section 7.4.3 will be used to impute partial dates).

Subgroup analyses will also be performed based on the main subgroups outlined above for ORR. Kaplan-Meier curves will be plotted for each subgroup.

7.5.3.4 *Time to Response*

TTR will be summarized similarly to DOR using the Kaplan-Meier method and estimates will be presented along with Brookmeyer-Crowley 95% CIs. Appropriate landmark estimates will also be included.

The following sensitivity analyses will be conducted:

- The TTR analysis will be repeated using the PP analysis set;
- The TTR analysis will be repeated using unconfirmed response;
- The TTR analysis will be repeated using central read based on confirmed response;
- The TTR analysis will be repeated using central read based on unconfirmed response.

Subgroup analyses will also be performed based on the main subgroups outlined above for ORR. Kaplan-Meier curves will be plotted for each subgroup.

7.5.3.5 *Disease Control Rate*

DCR will be summarized similarly to ORR.

The following sensitivity analyses will be conducted:

- The DCR analysis will be repeated using the PP analysis set;
- The DCR analysis will be repeated using unconfirmed response;
- The DCR analysis will be repeated using central read based on confirmed response;

□

The DCR analysis will be repeated using central read based on unconfirmed response.

Subgroup analyses will also be performed based on the main subgroups outlined above for ORR. The results will be displayed graphically in forest plots.

7.5.3.6 *Change in EORTC QLQ-C30*

EORTC QLQ-C30 functional scales (physical, role, emotional, cognitive, and social), symptom scales (fatigue, pain, and nausea and vomiting), global health status / QoL scale, and single items assessing additional symptoms commonly reported by cancer patients (dyspnoea, loss of appetite, insomnia, constipation and diarrhoea and perceived financial impact of the disease) will be summarized using descriptive statistics (mean, SD, median, 25th (Q1) and 75th (Q3) quartiles, and minimum/maximum values). Descriptive statistics will be calculated for observed values and change from baseline at each visit where the EORTC QLQ-C30 is assessed.

7.5.4 *Statistical/Analytical Issues*

7.5.4.1 *Adjustments for Covariates*

No covariate adjustments are planned.

7.5.4.2 *Handling of Dropouts or Missing Data*

The primary analysis of ORR will consider a subject with no evaluable response data to be a non-responder.

Every effort will be made to determine each subject's progression and survival information. However, subjects may withdraw their consent at any time from further participation in the study. Subjects may withdraw consent from treatment, survival follow-up, or both.

In analyses presented over time by visit, no imputations will be performed on missing data. All analyses will be based on observed data only. The effective sample sizes at each assessment visit will be based on the total number of subjects with non-missing data for the parameter of interest at that visit.

Unless otherwise specified, the following general imputation rules will be used for missing data in the assessment of an event:

If all parts of the date are missing, the date will not be imputed. In the case where only the start day of an event is missing, it will be replaced by the start day of study treatment

□

if the event occurs in the same month and year. Otherwise, it will be replaced by the first of the month. If the stop day is missing and the month is equal to the month of the last date of study treatment, the stop day of the event will be replaced by the stop day of study

treatment. Otherwise, the last day of the month will be used to replace the missing stop day.

If both the start day and month of an event are missing, the start day and month will be replaced by the start day and month of study treatment if the event and the start of the treatment occur in the same year; otherwise, it will be replaced by 1st of January. All imputed dates will have to be prior to the dates of withdrawal of consent, lost to followup, and death.

7.5.4.3 *Interim Analyses and Data Monitoring*

Throughout the study, a DMC will monitor safety parameters at regular intervals (approximately quarterly) after at least 3 subjects have been treated for at least 1 cycle. There was no formal interim analysis undertaken. Multicenter Studies

This is a multicenter study. Sites in North America, Europe, and Canada are expected to participate. All data collected from all study centers will be pooled for data analysis.

7.5.4.4 *Multiple Comparisons/Multiplicity*

No adjustments for multiple comparisons will be made. A single primary endpoint has been identified and each cohort is viewed as a separate study. No adjustment among secondary endpoints will be made as this study is exploratory.

7.5.4.5 *Use of an “Efficacy Subset” of Subjects*

The efficacy analysis will be performed on the Efficacy Evaluable analysis set since this population is the subset of the Safety analysis set who have measurable disease at baseline and have at least one post-baseline on-study assessment of tumor response.

The PP analysis set will be utilized as a sensitivity analysis. The PP analysis set will exclude subjects with major protocol violations as determined by the Sponsor prior to database lock.

7.5.4.6 *Active-Control Studies Intended to Show Equivalence*

This study does not include an active-control product and is not intended to demonstrate equivalence between any two drug products.

7.5.4.7 *Examination of Subgroups*

The primary and secondary efficacy endpoints (excluding the QoL data) will be summarized by various subgroups of interest. The subgroups are defined in Section 7.5.2.

Additional subgroup analyses may be performed post-hoc, as appropriate.

